### Secondary outcomes

"Definite relapse" and "probable relapse" will be separate secondary outcomes, each assessed at 21 days and 28 days after antibiotic completion. [This was originally "definite or probable relapse"].

Episodes of relapses (# 1-4) will be analyzed both as per protocol and as per intention-to-treat:

1. "Definite relapse": by 21 days after antibiotic completion.

2. "Probable relapse": by 21 days after antibiotic completion.

3. "Definite relapse": by 28 days after antibiotic completion.

4. "Probable relapse": by 28 days after antibiotic completion.

Episodes of relapses (# 5-7) will be analyzed as per intention-to-treat:

5. "Definite or probable relapse" in the 28-day period after randomization and 35-day period after randomization

6. "Definite" in the 28-day period after randomization and 35-day period after randomization

7. "Probable" in the 28-day period after randomization and 35-day period after randomization]

The following will also be analysed in the 35-day period of observation after randomization:

(A) Episodes of secondary infections during the observation period. These may be bacterial or fungal.

(B) Adverse events: All fresh adverse events occurring after randomisation would be recorded. Adverse events with onset prior to randomisation would be recorded only if there is worsening after randomisation. Adverse events are listed and defined as per Appendix 5.

### **Sample Size Calculation**

The sample size was calculated to be 350 in each arm based on the following assumptions: Event rate for the composite primary outcome of "definite or probable relapse" assumed to be 10% (combining both 7- and 14-day treatment arms) based on the earlier study (Chaudhary G, Dutta S, Narang A, Journal of Tropical Pediatrics 2006), non-inferiority margin of 7%, one sided alpha level as 5% and power of 90% and loss to follow- up of approximately 10%.

### Mid-term analysis and stopping rules

The original was: Mid-term analyses will be performed after a total of one-third and two-third subjects are recruited. A separate Data Safety Monitoring Board will monitor serious adverse events in the trial and perform mid-term analyses at 1/3rd and 2/3rd recruitment. O'Brien-Fleming stopping rules and p values for superiority will be used for the interim analyses.

Data Safety Monitoring Board revised it to: DSMB will monitor serious adverse events in the trial and perform one interim analysis. The timing of this analysis would be based on either of the following: when about 50% of the expected primary outcomes have occurred (expected outcome events for the entire trial is 100 and therefore first interim analysis will be when approximately 50 events have occurred) or when 350 subjects have completed their follow-up as per protocol whichever is earlier. At the time of interim analysis, the DSMB will revisit the sample size of the study. O'Brien Fleming stopping criteria would be used for the primary outcome while Pocock's stopping rule for the serious adverse events.

If treatment failure rates are found significantly higher in the 7-day group in mid-term analysis, the trial will be stopped. If a death occurs due to bacteriologically confirmed relapse from the same organism Version dated 26 Sep 2019

during the 28-day follow-up, the allocation group of that subject will be immediately ascertained. If it happens to be in the 7-day group, the trial will be stopped. The Data Safety Monitoring Board will also decide whether a death or other serious adverse event can be attributed to the intervention in the randomized controlled trial, and what compensation, if any, should be awarded.

[figure not shown]

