Title:

Comparison of the Efficacy of a 7-day Versus 14-day Course of Intravenous Antibiotics in the Treatment of Uncomplicated Neonatal Bacterial Sepsis: a Randomized Controlled Noninferiority Trial

NCT number: NCT 03280147

Date of document: 26 September 2019

STATISTICAL ANALYSIS PLAN

The baseline variables shall be described using descriptive statistics. Categorical variables will be described by percentages. Numerical variables will be described as mean (standard deviation) or median (1st, 3rd quartile), depending on distribution. Normality of distribution of numerical variables will be tested by Shapiro Wilk test and QQ plot.

The primary outcome variable is "definite or probable relapse" within 21 days after stopping antibiotics. Secondary outcome variables include individually definite and probable relapse within 21 days and 28 days after stopping antibiotics; definite and probable relapse within 28 days and 35 days after randomization; "definite or probable relapse" within 28 days and 35 days after randomization; secondary bacterial infections within 35 days after randomization and adverse events within 35 days after randomization. Analysis will be both per protocol as well as intention-to-treat, as this is a noninferiority trial.

As all the outcome variables are categorical, chi-square test with Yates correction or Fisher's Exact test, as applicable, will be used to compare the 2 groups.

Sub-group analysis has been planned for the following sub-groups: birth weight 1000-1499 grams, 1500 to 2000 grams, and >2000 grams, those infected with gram positive organisms versus the rest and those with radiological pneumonia versus those without radiological pneumonia. A p-value for the test of interaction (Breslow-Day test) will be derived for the subgroup analyses.

Multi variable logistic regression analysis will be performed to determine the relationship between group membership (7-day course of antibiotics versus 14-day course of antibiotics) and the primary outcome after adjusting for the following baseline covariates: birth weight, age of neonate, infection with gram positive organisms, number of days by which clinical remission of sepsis achieved prior to randomization.

Mid-term analyses will be performed by an independent Data Safety Monitoring Board at 1/3rd and 2/3rd of expected recruitment.

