Data Safety Monitoring Board will monitor serious adverse events in the trial. O'Brien-Fleming's stopping criteria will be used for the primary outcome while Pocock's stopping rules will be used for serious adverse events.

Analysis shall be done using the statistical software packages SPSS version 22.

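### The protocol has one interim analysis and the SAP two, the harm stop has no stated alpha or sidedness, and the 100 expected events do not match the assumed 10% rate

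*Protocol*

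**What the plan says.** **Number of looks.** The protocol section on mid-term analysis and stopping rules first gives the original plan, with looks at one third and two thirds of recruitment. It then gives the board's revision: "DSMB will monitor serious adverse events in the trial and perform one interim analysis". The look falls at about 50 events or "when 350 subjects have completed their follow-up as per protocol whichever is earlier". That page is marked 26 September 2019. The SAP carries the same date and says, as its own plan: "Mid-term analyses will be performed by an independent Data Safety Monitoring Board at 1/3rd and 2/3rd of expected recruitment".

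**Boundaries.** The two documents agree on the families. In the SAP's words, "O'Brien-Fleming's stopping criteria will be used for the primary outcome while Pocock's stopping rules will be used for serious adverse events". The protocol adds the action: "If treatment failure rates are found significantly higher in the 7-day group in mid-term analysis, the trial will be stopped". The text of neither gives the alpha, the sidedness or a critical value for the interim test. One figure in the protocol section could not be seen. One-sided 5% appears only among the inputs to the sample size, where it belongs to the non-inferiority test.

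**Expected events.** The sample size section takes the event rate as "assumed to be 10% (combining both 7- and 14-day treatment arms"), with 350 infants per arm. The interim section says: "expected outcome events for the entire trial is 100 and therefore first interim analysis will be when approximately 50 events have occurred". It also says: "At the time of interim analysis, the DSMB will revisit the sample size of the study".

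**The concern.** A board holding both documents cannot tell whether to look once or twice, and the dates do not settle it. The SAP pairs the old schedule with the revised split of O'Brien-Fleming for the primary outcome and Pocock for serious adverse events, so it mixes two stages of the plan. In the protocol, the word that numbers the single interim as the first adds to the doubt.

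This matters because the trial stops when failures are significantly more frequent in the 7-day group. What counts as significant depends on the number of looks, the alpha and the sidedness.

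The event count is a separate, smaller matter. If 100 is wrong, the event trigger does not mark the halfway point it claims to mark. If 100 is right, the 10% behind the sample size is not the rate the board expects, and the stated power does not hold.

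**Working it through.** **1. Reproduce the sample size.** Inputs from the protocol's sample size section: 10% in both arms, margin 7 percentage points (absolute scale assumed), one-sided 5%, power 90%, loss 10%.

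n per arm = 2 × 0.10 × 0.90 × (1.645 + 1.282)² / 0.07² = 314.6, so 315; 315 / 0.9 = 350. The stated figure is reproduced, giving 700 randomized and 630 evaluable.

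**2. Expected events from the same inputs.**
- 700 × 0.10 = 70; 630 × 0.10 = 63.
- 50 / 70 = 71%; 50 / 63 = 79%.
- 100 events would need a rate of 100/700 = 14.3% or 100/630 = 15.9%.
- Power with 315 per arm = Φ(0.07 / √(2p(1−p)/315) − 1.645): 90.0% at 10%, 80.7% at 14.3%, 77.6% at 15.9%.

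**3. Which trigger comes first.** At 10%, 350 completers yield about 35 events. The binomial chance of 50 or more events among 350 is 0.7% at a 10% rate. At assumed rates of 12%, 15% and 20% it is 11%, 67% and 99.8%.

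**4. Boundaries under each schedule.** Overall one-sided 5% is assumed. O'Brien-Fleming limits are z = c/√t, and Pocock limits are a constant z, each solved so that the chance of crossing at any look, the final one included, is 5%. The protocol's look is placed at 350/630 = 56% of evaluable infants.

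| Schedule | O'Brien-Fleming interim z | Interim p limit | Pocock p per look |
|---|---|---|---|
| Protocol, one look at 56% | 2.264 | 0.0118 | 0.0311 |
| SAP, looks at 1/3 and 2/3 | 2.961, 2.094 | 0.0015, 0.0181 | 0.0232 |

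With the single look placed at 50% (350 of 700), the limits are 0.0088 and 0.0304. At two-sided 5%, the O'Brien-Fleming limit at 56% falls to 0.0039 in one tail, so sidedness alone changes it threefold.

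**5. What this means in relapses.** Yates z = [(|a − b| − 1)/n] / √(2 × 0.10 × 0.90 / n), at a pooled rate of 10%. One third and two thirds of 700, less 10% loss, give 105 and 210 per arm, assuming all those recruited have been followed.
- Protocol, 175 per arm: 25 v 10 stops (z 2.494); 24 v 11 does not (2.138).
- SAP first look, 105 per arm: 18 v 3 stops (3.220); 17 v 4 does not (2.760).
- SAP second look, 210 per arm: 28 v 14 stops (2.114, limit 2.094).

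**6. Effect on the non-inferiority claim.** Set the true difference at the margin, with 315 per arm and 10% variance. The standard error is √(0.18/315) = 0.0239, and 0.07/0.0239 = 2.928. Non-inferiority is claimed at the end if the trial was not stopped for harm and the final z for 7-day excess is below 2.928 − 1.645 = 1.283. With the final test kept at 5%, the chance of a false claim is 4.94% with the protocol's one look and 4.92% with the SAP's two. Power with no true difference is 89.8% under both schedules, against 90.0% with no interim.

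**The case against.** **The SAP sentence is only a carry-over.** The protocol labels the one-third and two-thirds looks as the original plan and names the board as the author of the change, so a careful reader can guess which text is meant. That lowers the severity. The SAP still states two looks as current text, so the conflict stands.

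**Missing boundaries are detail.** This largely stands. Both documents name a family for each endpoint, and the limits follow once the schedule, alpha and sidedness are fixed. The real gap is narrower: which hypothesis the interim tests, at what alpha, and in how many tails. The superseded text referred to superiority p values; the revision is silent.

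**The stronger reading on error rates.** A reader might infer that the mismatch inflates the trial's type I error, or that the final non-inferiority test must give up alpha. One-look limits used at the SAP's two looks, with a final look as well, do give a total one-sided error of 5.5% (O'Brien-Fleming) or 6.6% (Pocock). But these are rates for wrongly declaring 7 days worse, and they include a final harm test. The only comparative stop spelled out for the primary outcome is against the 7-day arm. Such a stop allows no early non-inferiority claim, and step 6 shows the false-claim rate slightly below 5%.

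**The 100 may have a basis.** Under the intention-to-treat rule, lost 7-day infants count as relapses; 35 of these plus 63 observed events gives 98. No passage says this was done, and imputed failures do not occur during follow-up. The fair description is that 100 is underived and does not match the 10% rate. A reader might also infer that the error seriously mistimes the interim, but at 10% the 350-completer trigger governs.

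**Conclusion.** Two defects hold, and both should be fixed.

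- **Interim schedule.** The documents conflict on one look or two, and neither states the hypothesis, alpha and sidedness of the primary-outcome stop. Under one-sided 5%, the p limit in force at a look could be 0.0118, 0.0015 or 0.0181. The consequence is how readily the board stops for harm.
- **Event count.** The sample size inputs give 70 events (63 evaluable), not 100, so 50 is 71–79% of the total. The practical effect on timing is small at 10%. If 100 is intended, power is 78–81%, not 90%.

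The integrity of the non-inferiority test is not at issue, provided no early claim in favour of 7 days is allowed; the documents describe none. The boundary figures rest on one-sided 5% applying at the interim and on 350/630 as the information fraction.

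**What to change.** 1. **SAP:** replace the sentence on looks at one third and two thirds with the protocol's single board interim and its two triggers. In the protocol, delete the word that numbers this interim as the first.
2. **Both documents:** state that the primary-outcome interim is a test for harm (7-day worse), give its alpha and sidedness, and say that the final non-inferiority test keeps its one-sided 5% because no early non-inferiority claim is allowed.
3. **Both documents:** choose one boundary method and keep to it. Classical and spending-function limits differ. Because the look time varies, an O'Brien-Fleming-type spending function at the actual information fraction suits the primary outcome, and a Pocock-type one suits serious adverse events. At 350/630 and one-sided 5% the interim p limits would be 0.0085 and 0.0335. Spending handles timing; it does not by itself cover a sample size change prompted by the by-arm results.
4. **Protocol:** correct the expected total to 70 (63 evaluable) and drop the statement that 50 is half. Otherwise, state the basis of 100 and restate the event rate and power. Whether the event trigger changes is for the board.

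The cost is one replaced SAP sentence, one deleted word, one corrected or justified figure, and a short statement of the interim test in each document. The sample size and the 350-completer trigger stay. The limit must be computed when the look takes place.

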# Data analysis

The baseline variables shall be described using descriptive statistics. As all the outcome variables are categorical,  $x^2$  test with Yates correction or Fisher's Exact test as applicable will be used. Sub-group analysis has been planned for the following sub-groups: 1000-1500 g, 1501-2000 g, >2000 g, those infected with gram positive organisms and those with radiological pneumonia. For the sub-group analyses, level of significance will be kept as p< 0.01. Analysis shall be done using the statistical software packages SPSS version 10.

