### METHODS

#### Study design

This is a multi-centric, randomized, active-controlled, non-inferiority trial. Stratification of subjects is done according to center and birth weight.

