# Not eligible for randomization

- Sterile blood culture
- Suspected contaminants in blood culture.
- Growth of Staphylococcus aureus in blood culture
- Growth of fungal organism in blood culture
- Diagnosis of meningitis, septic arthritis, osteomyelitis, abscess
- Has not gone into remission on day 5 or have recurrence of symptoms from day 5 through day 7
- If the empiric antibiotic is resistant but neonate has shown improvement of signs and symptoms of sepsis and there is ambiguity regarding in vivo sensitivity of antibiotic use

These elaborate criteria have been drawn up because this is an equivalence (non-inferiority) trial. In an equivalence trial, extra care has to be taken to exclude subjects who are likely to respond irrespective of which treatment arm they are in and also subjects who are not likely to respond irrespective of which treatment arm they are in. This is because inclusion of such patients would bias the results towards no effect (ie equivalence).

Data from enrolment until the point of determining eligibility for randomization will be recorded in the "Enrolment sub-form" of Proforma A of the case report form.

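### Subgroups in this non-inferiority trial are judged only by tests for a difference (at p<0.01 in the protocol) and by an interaction p-value, never against the 7-point margin

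*Protocol*

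**What the plan says.** The protocol's Study design section states the objective: "This is a multi-centric, randomized, active-controlled, non-inferiority trial". Sample Size Calculation sets a margin of 7 percentage points at a one-sided 5% level. The margin appears nowhere else in either document.

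The protocol's Data analysis section treats every outcome as categorical and says that the chi-square "test with Yates correction or Fisher's Exact test as applicable will be used". These tests ask whether the arms differ and contain no margin. The subgroups listed are "1000-1500 g, 1501-2000 g, >2000 g, those infected with gram positive organisms and those with radiological pneumonia". One rule is attached to them: "For the sub-group analyses, level of significance will be kept as p< 0.01". No reason for that level is given, and its sidedness is not stated.

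The SAP plans the same tests for comparing the groups. For subgroups it adds: "A p-value for the test of interaction (Breslow-Day test) will be derived for the subgroup analyses". It gives no level for that p-value and is silent on 0.01. Neither document mentions a confidence interval, for subgroups or for the trial as a whole, and neither says how a non-significant subgroup result will be interpreted.

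**The concern.** Lowering the significance level protects against wrongly claiming a difference. In a non-inferiority trial the error that matters more is failing to see that the shorter course is worse in some group of infants. For that error, a difference test in a small subgroup is weak, and a stricter level makes it weaker.

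The stake is what a reader can learn from the subgroup table. A line showing only p≥0.01 fits a subgroup in which 7 days is as good, a subgroup in which it is worse by the whole margin, and a subgroup too small to say. An interval set against the margin separates these; a p-value for a difference does not.

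**Working it through.** **Inputs from the protocol.** Relapse 10% (both arms combined), margin 7 points, one-sided alpha 5%, power 90%, loss about 10%, 350 per arm (Sample Size Calculation); 1:1 allocation (Randomization procedure); Yates chi-square and p<0.01 (Data analysis).

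**Assumptions not in the documents.** Subgroup sizes are not given. I use 63, 105 and 158 evaluable infants per arm: a fifth, a third and a half of 315. I take p<0.01 as two-sided, and relapse on 14 days as 10%.

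**Step 1: the plan's own figure.** n = (1.645 + 1.282)² × (0.10×0.90 + 0.10×0.90) / 0.07² = 314.6, so 315 evaluable per arm; 315/0.90 = 350. The stated sample size reproduces exactly.

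**Step 2: chance that the test misses harm equal to the margin.** For A relapses on 7 days and B on 14 days, n per arm, N = 2n and m = A + B, the Yates statistic is

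X² = N × (n|A − B| − N/2)² / (n² × m × (N − m)),

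compared with 3.841 (p<0.05) or 6.635 (p<0.01). Power is the sum of the binomial probabilities of all tables that reject with A > B. The chance of a non-significant result is taken as 1 − power.

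| Per arm | 17% vs 10%: missed at 0.05 | missed at 0.01 | 24% vs 10%: missed at 0.05 | missed at 0.01 |
|---|---|---|---|---|
| 63 | 86% | 96% | 53% | 76% |
| 105 | 76% | 91% | 27% | 52% |
| 158 | 62% | 83% | 10% | 26% |

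At harm equal to the margin, moving from 0.05 to 0.01 adds about 10 to 21 points to a miss rate that is already 62–86%. Because the protocol's 10% is a combined rate, I also checked 13.5% vs 6.5% at 105 per arm: missed 70% at 0.05 and 88% at 0.01.

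**Step 3: what the rule means in counts.** With 105 per arm and 11 relapses on 14 days:
- 23 on 7 days is the smallest count significant at 0.05 (X² = 4.25), an excess of 12/105 = 11.4 points.
- 27 is the smallest significant at 0.01 (X² = 7.23), an excess of 16/105 = 15.2 points, more than twice the margin.
- 26 vs 11 gives X² = 6.43, not significant at 0.01. Its risk difference is 15/105 = 14.3 points, with standard error √(0.248×0.752/105 + 0.105×0.895/105) = 0.0516. The 90% interval is 14.3 ± 1.645×5.16, or 5.8 to 22.8 points. The interval shows the problem; the planned p-value alone reports a non-significant subgroup.

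**Step 4: the same harm judged by an interval.** With relapse of 17% vs 10%, the upper limit of a two-sided 90% Wald interval falls below 7 points about 5% of the time at all three sizes (0.054, 0.055, 0.054). If relapse is truly 10% in both arms, it falls below 7 points 38%, 53% and 67% of the time. The interval seldom clears a harmed subgroup, but it is often inconclusive for an unharmed one.

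**The case against.** **The 0.01 level has a proper purpose.** Treating the five subgroup tests as independent, the chance of at least one false claim of a difference is 1 − 0.95⁵ = 22.6% at 0.05 and 1 − 0.99⁵ = 4.9% at 0.01. This stands as a reason to keep 0.01 for claims of a difference. It does not make the test informative about non-inferiority.

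**No passage says that p≥0.01 means no difference.** This stands. A reader might infer that the plan would pass off a harmed subgroup as equivalent, but neither document contains such a rule. The protocol's warning that "inclusion of such patients would bias the results towards no effect (ie equivalence" concerns who is randomized and does not bear on the subgroup level; it shows only that the authors know which direction of bias matters.

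**The 0.01 level is not the main cause.** This also stands. At 0.05 the same test already misses harm equal to the margin 62–86% of the time.

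**The SAP already adds an interaction test.** True, and it can coexist with a within-subgroup level, so the two documents are unaligned rather than contradictory. But the interaction test does not fill the gap. A simulated log-odds-ratio interaction test (two-sided 0.05, the rest of the 315 per arm at 10% in both arms) had power of about 15%, 20% and 22% at 63, 105 and 158 per arm for 17% vs 10%.

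Had 0.01 been meant for a confidence bound against the margin, it would be stricter on the 7-day course (about 1% wrongly passed instead of about 5%). The Data analysis section, which names only difference tests, does not support that reading.

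**Conclusion.** The concern holds in this form: the plan gives no means of judging a subgroup against the margin that the trial is built on. Under the stated assumptions, a subgroup harmed by the full margin is non-significant 83–96% of the time at p<0.01 and 62–86% at p<0.05. The 0.01 level aggravates a weakness that comes mainly from small subgroups and the choice of a difference test.

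It would go too far to say that any subgroup harmed beyond the margin would almost certainly be missed. At twice the margin (24% vs 10%), power at p<0.01 is 24%, 48% and 74% at 63, 105 and 158 per arm. Nor do the documents identify one weight band as the most exposed, since they give neither subgroup sizes nor subgroup risks.

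The percentages rest on assumed sizes and rates. The conclusion that a non-significant result says little holds at all three sizes for harm equal to the margin.

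**What to change.** In both documents:

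1. For every subgroup level, report the number of infants and relapses per arm and the risk difference (7-day minus 14-day) with a two-sided 90% confidence interval, which matches the one-sided 5% level, beside the 7-point margin.
2. Keep the SAP's interaction p-value next to these intervals and carry it into the protocol.
3. State that a non-significant subgroup difference is not evidence of non-inferiority.
4. Say in both documents whether the 0.01 level applies. If it is kept, limit it to a multiplicity guard for claims of a difference.

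The cost is a few sentences, with no extra infants or data. The intervals will be wide, will often cross the margin even without harm (Step 4), and are not adjusted for multiplicity, so they should be labelled exploratory.
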